# Appendix 5 Questionnaires

The COPD Assessment TestTM was developed by a multi-disciplinary group of international experts in COPD supported by GSK. The CAT is self-administered on paper. CAT, COPD Assessment Test, and the CAT logo are trademarks of the GSK group of companies. GlaxoSmithKline Services Unlimited. Registered in England.

### COPD Assessment TestTM (CAT)

https://www.catestonline.org/patient-site-test-page-english.html

Accessed 01April2024.

CAT score	Level of Impact
31 - 40	Very High Impact
21 - 30	High Impact
10 - 20	Medium Impact
< 10	Low Impact

The modified Medical Research Council (mMRC) Dyspnea Scale (From ATS News 1982; 8:12-16.8). The mMRC is based off the MRC breathlessness score first published by Fletcher, et al.

Site staff will administer/interview the subject to complete the mMRC dyspnea scale questionnaire.

mMRC Grade	Description
0	Not troubled with breathlessness except with strenuous exercise
1	Troubled by shortness of breath when hurrying on the level or walking up a slight hill
2	Walks slower than people of the same age on the level because of breathlessness or has to stop for breath when walking at own pace on the level
3	Stops for breath after walking about 100 yards or after a few minutes on the level
4	Too breathless to leave the house or breathless when dressing or undressing

### **1** Abbreviations

AE	Adverse Event
ATC	Anatomical Therapeutic Chemical
BID	Twice daily
BMI	Body Mass Index
CAT	COPD Assessment Test
CI	Confidence Interval
COPD	Chronic Obstructive Pulmonary Disease
EOT	End of Treatment
FAS	Full Analysis Set
$FEV_1$	Forced Expiratory Volume in 1 Second
GOLD	Global Initiative for Chronic Obstructive Lung
	Disease
ICS	Inhaled Corticosteroid(s)
LABA	Long-Acting β2 Agonist
LAMA	Long-Acting Muscarinic Antagonist
LSM	Least Square Mean
MedDRA	Medical Dictionary for Regulatory Activities
mMRC	Modified Medical Research Council Dyspnea Scale
PDE	Phosphodiesterase
PT	Preferred Term
SAE(s)	Serious Adverse Event(s)
SAP	Statistical Analysis Plan
SAS®	Statistical Analysis Software®
SAS	Safety Analysis Set
SD	Standard Deviation
SOC	System Organ Class
TEAE	Treatment-Emergent Adverse Event(s)
WHO	World Health Organization
WOCBP	Women of Childbearing Potential

# 2 Introduction

### 2.1 Background

Chronic obstructive pulmonary disease (COPD) is characterized by progressive airflow obstruction which is largely irreversible. COPD is predicted to be the third leading cause of death and fourth most common cause of disability worldwide by 2030 (Stuckler, 2008). The primary goals of pharmacological treatment of COPD are to reduce symptoms, exacerbation frequency and exacerbation severity as well as to improve overall quality of life in patients with COPD. Current standard-of-care treatments include inhaled short- and long-acting bronchodilators (i.e., muscarinic antagonists [LAMA] and  $\beta$ 2 agonists [LABA]) and inhaled corticosteroids (ICS) are utilized to manage symptoms of COPD (GOLD, 2024).

Statistical Analysis Blan	Client/Project	Verona Pharma/RPL554-CO-303
Statistical Analysis Plan	Version and Date	V02 12/11/2024

Tools to assess if treatment goals are attained include several patient-reported outcome questionnaires to assist in communications between the patient and physician. However, the uptake of these questionnaires into routine clinical practice is integral to the assessment of individualized treatment regimens (Stanford, et al., 2019). The COPD Assessment Test [CATTM; CAT] (Jones, et al., 2009) is a validated, short, and simple patient completed questionnaire. The CAT is often used in a clinical setting to assess further the COPD symptoms and impact of a patient's well-being.

Verona Pharma plc. is developing inhaled nebulized ensifentrine for the maintenance treatment of chronic obstructive pulmonary disease (COPD). Ensifentrine is a novel, small molecule, potent, and selective dual inhibitor of Phosphodiesterase 3 (PDE3) and PDE4. The dual mechanism of action of ensifentrine has both bronchodilatory and anti-inflammatory effects and has the potential to offer an important maintenance treatment option for the treatment of obstructive and inflammatory diseases of the respiratory tract, such as COPD, cystic fibrosis, and asthma (Donahue et al., 2023). Ensifentrine has been evaluated in 22 completed clinical studies involving approximately 3,000 subjects, of which 16 studies involving over 2,800 subjects comprise the COPD development program including pharmacokinetic, pharmacodynamic, Phase IIb, and Phase III studies. In two Phase III studies (RPL554-CO-301 [n=760] and RPL554-CO-302 [n=789]) ensifentrine (3 mg) treatment consistently demonstrated the bronchodilator profile of ensifentrine in subjects with moderate to severe COPD over 12 weeks while significant effects were shown across all key  $FEV_1$  endpoints and a significant improvement in exacerbation frequency and severity was shown in both studies (Anzueto, et al., 2023). This Phase IIIb study will assess the effect of ensifentrine on CAT scores in subjects with moderate to severe COPD when added to standard of care in routine clinical practice.

### 2.2 Changes to Planned Analyses

Not applicable as this is the initial version of the SAP.

# 3 Study Objectives

The objectives for this study are as follows:

Primary Efficacy Objective: The primary efficacy objective for this study is to assess the proportion of responders to treatment with ensifentrine, defined as subjects with an improvement in individual CAT scores of  $\geq 2$ , when added to standard of care in symptomatic subjects with moderate to severe COPD in routine clinical practice.

Secondary Efficacy Objective: To investigate the effects of ensifentrine on COPD symptoms, as measured by the CAT in symptomatic subjects with moderate to severe COPD when added to standard of care in routine clinical practice.

Safety Objective: To summarize the safety profile of subjects treated with ensifentrine.

# 4 Investigational Plan and Study Design

This is a Phase IIIb, single-center, open-label study investigating the effect of treatment with twice daily nebulized ensifentrine (3 mg) over 12 weeks on CAT scores in subjects with moderate to severe COPD when added to standard of care in routine clinical practice.

At Visit 1, potential subjects will be provided with the informed consent for participation in the study. Following signature on the informed consent, the following information will be collected, and procedures performed to confirm subject eligibility for participation in the study in the following sequence:

- CAT Training followed by subject completion of the CAT on paper
- Modified Medical Research Council Dyspnea Scale (mMRC)
- Collect and record demographic data
- Eligibility review (inclusion and exclusion criteria)
- Review and record medical, surgical, COPD and smoking history
- Review of prior and concomitant medication

At Visit 2, subject eligibility will be confirmed (screening tests will be verified, and it will be assured that the subject meets all inclusion criteria, and no exclusion criteria). Subjects who are screen failures may be rescreened with approval from the Medical Monitor. Rescreened subjects should be assigned a new subject number different from the initial screening event. Spirometry will be performed, a physical examination completed, and vital signs will be assessed. Eligible subjects will receive a nebulizer and compressor and will be administered their first dose of ensifentrine (3 mg) in-clinic during training on nebulizer use. Adverse events will be assessed. Subjects will receive a 6-week supply of ensifentrine (3 mg) to be administered twice-daily (BID) with a standard jet nebulizer. Ensifentrine will be administered BID for a total of 12 weeks.

At Visit 3 (Week 6), subjects will return and complete the CAT first, their concomitant medication will be reviewed, their vital signs and safety will be assessed. Subjects will receive a 6-week supply of ensifertrine (3 mg) administered BID.

At Visit 4 (Week 12), subjects will complete the CAT first, their concomitant medication will be reviewed, their vital signs and safety will be assessed. After 12 weeks, treatment with nebulized ensifentrine (3 mg) will end.

A follow-up phone call will be made to the subject approximately one week after the end of treatment.

Subjects may remain on prescribed short- and long-acting COPD medications throughout participation provided they are not included in the prohibited medication list. COPD exacerbations should be treated at physician's discretion as per usual practice.

A subject is considered to have completed the study if he/she has successfully completed all scheduled visits and completed follow-up contact. With no rescheduled visits, the study should last approximately 14 weeks.

# 5 Sample Size Justification

A sample size of approximately 20 subjects provides the ability to demonstrate a responder proportion estimate statistically differs from zero. Assuming a 30 percent response rate in the study population, 20 subjects would provide an expected count of 6 events. The two-sided 95% confidence interval for the number of events generated via normal approximation is (1.199, 10.801). Thus,20 subjects provide the ability to demonstrate the derived proportion differs from zero determined by the lower two-sided 95% confidence limit derived from the estimated count using a normal approximation assuming a standard error equal to the square root of 6.

Twenty subjects also provide the ability to demonstrate the estimates of mean change from baseline does not extend to the clinically meaningful deterioration limit of (+2 units). Assuming estimated mean improvement of 1 unit with a corresponding standard deviation equal to 4.5, 20 subjects provide the ability to demonstrate the upper 95% confidence interval for a mean change from baseline estimate does not exceed 2 units.

**Statistical Analysis Plan** 

Client/ProjectVerona Pharma/RPL554-CO-303Version and DateV02 12/11/2024

# 6 Visit Schedule and Visit Windows

Table 1: Schedule of Assessments and Procedures

	Study Start		Treatment Period	p	Study End	Early Withdrawal Termination ¥	ly Withdrawal / Cermination ¥
	Screening	Day 1 (≤7 days)	Week 6 (42 ± 3 days)	Week 12 (42 ± 3 days)	7 ± 3 days after Visit 4	As Soon as Possible after EW/T	7±3 days after EW/T Visit
	Visit 1	Visit 2	Visit 3	Visit 4 (EOT)	Follow-up	EW/T Visit	Follow-Up
Informed consent A	Х						
Inclusion/exclusion criteria (eligibility review)	Х	Review, Update					
Demographics (date of birth, age, gender, race, ethnicity)	Х						
CAT TM training	Х						
CAT TM B	X*		X*	X*			
mMRC (administered by study team)	х						
Medical, surgical, smoking history	Х	Review, Update					
Prior and concomitant medication	Х						
Vital signs (blood pressure and pulse rate)		Х	Х	Х		Х	
Height and Weight; BMI calculated		Х					
Brief physical exam c		Х					
Urine pregnancy test D		Х	Х	X			
Pre- and post-bronchodilator Spirometry E		Х					
Nebulizer equipment materials dispensing, review, and training; collection at end F		Х		X			
Study medication dispensing G		Х	X				
In clinic study medication dosing		X					
Concomitant medication review		Х	Х	Х	X	Х	Х
Study medication compliance			Х	Х		Х	
AE and SAE recording		Х	Х	Х	Х	Х	Х
Phone call to subject					Х		Х

Plan	
Analysis	
Statistical	

rerona Ph	V02 12/11/2024
Jerona Pharma/RPL554-CO-303	1/2024

The CATTM is completed by the subject on paper first before any procedures and assessments. \*The early withdrawal / termination visit should be conducted as Note: Information and details on most of the Study Assessments and Procedures can be found in the protocol in Section Error! Reference source not found. soon as possible. If possible, subjects should remain on study medication through the early termination visit (protocol Section Error! Reference source not f ound.).

- Informed consent must be obtained by the process described in Error! Reference source not found. of the protocol. Consent must be obtained prior to any s tudy procedures being performed. Ą.
  - Following informed consent, the CATTM is performed first before any procedures and assessments. ы.
    - c. Assessments of the Cardiovascular, Respiratory, Gastrointestinal, and Neurological systems.
- Pregnancy Testing: Pregnancy testing will be conducted on women of childbearing potential only (refer to Error! Reference source not found. of the p rotocol) Ū.
- Spirometry: Pre-bronchodilator testing will be conducted prior to dosing with albuterol. Post-bronchodilator testing should be conducted between 15- and 30-minutes following administration of 4 puffs of albuterol. ங்
  - F. Collect study supplied compressor if allowed per local site practices.
- Information on study medication, dosing and compliance, nebulizers and compressor can be found in protocol Section Error! Reference source not found. Ŀ

Abbreviations: AE=Adverse Event; BMI= Body Mass Index; CATTM = COPD Assessment TestTM, COPD=Chronic Obstructive Pulmonary Disease; EOT=End of Treatment; mMRC=Modified Medical Research Council Dyspnea Scale; SAE=Serious Adverse Event; V=Visit; WOCBP=Women of Child-bearing Potential.

Statistical Analysis Dlan	Client/Project	Verona Pharma/RPL554-CO-303
Statistical Analysis Plan	Version and Date	V02 12/11/2024

# 7 Study Populations

Allocation of subjects to the analysis populations (and whether any subjects or specific data from a subject will be excluded) will be determined prior to database lock. Study populations will be defined as follows:

**Enrolled Analysis Set**: The Enrolled Analysis Set (EAS) will consist of all subjects who provided informed consent for this study. Subjects will be classified according to administration of study medication at study Day 1, and will be summarized with and without the administration of study medication.

Full Analysis Set: The Full Analysis Set (FAS) will consist of all subjects that were administered the study medication at Visit 2 and have a CAT completed at baseline and from at least one post-treatment visit. The full analysis set will be used for all efficacy analyses.

Safety Analysis Set: The Safety Analysis Set (SAS) will consist of all subjects who were administered the study medication at Visit 2. The safety analysis set will be used for all safety analyses and baseline summaries.

# 8 Statistical Methods

### 8.1 General Reporting Conventions

Study data will be made available in listings or electronic format as requested. Study results will be reported in tabular form using descriptive and inferential statistics. Standard numeric descriptive statistics include number observed (n), mean, standard deviation (SD), median, minimum, and maximum values. Standard categorical descriptive statistics include the count and percentages of subjects for each level of the variable summarized. Confidence intervals (CIs) will be two-sided 95% intervals. Unless specified otherwise, two-sided p-values of less than or equal to 0.05 or one-sided p-values of less than or equal to 0.025 will be considered statistically significant. All summaries and statistical analyses will be completed using Version 9.4 or later of the SAS Statistical Analysis System (SAS Institute, Inc. Cary, NC) for Windows x64.

### 8.2 Adjustments for Interim Analyses and Multiplicity of Endpoints

No interim analyses are planned for this study. As there is only one primary efficacy endpoint, no adjustments will be made for multiplicity.

### 8.3 Handling of Missing Data

As discontinuation of study medication will result in subject withdrawal, data collected after treatment withdrawal will not be included in the analyses, and missing data will not be imputed.

### 8.4 Evaluations and Statistical Analyses

### 8.4.1 Subject Disposition

Study disposition will be summarized overall and presented in listing format. Disposition and baseline information will be summarized using the Enrolled population. For subjects undergoing more than 1 screening assessment, the last screening assessment will be included in disposition summaries. Study disposition information will be summarized through:

- Number of subjects screened.
- Number of screen failures and reason for failure.
- Number of subjects in each analysis population (EAS, FAS, and SAS).
- Number of subjects that completed the study.
- Number of subjects that completed each follow-up visit (Day 1, Week 6, Week 12, Follow-up phone call)
- Number of discontinued subjects and reason for discontinuation.
- Duration of follow-up in days summarized as a continuous variable.

Additionally, the number of subjects with major protocol deviations will be summarized by deviation type and category of violation overall. Major protocol deviations will also be included in subject listings.

### 8.4.2 Demographics and Baseline Characteristics

Demographics and baseline data including age, gender, race, ethnicity, height, weight, and BMI will be summarized descriptively overall and presented in listing format for the Safety Analysis Set. Medical history will be coded using MedDRA and summarized descriptively by SOC and PT for the Safety Analysis Set. Medical history will be provided in subject listings for the Safety Analysis Set. COPD history including COPD type, COPD diagnosis history, and COPD exacerbation history will be summarized descriptively and presented in listing format for the Safety Analysis Set. Smoking history will be summarized descriptively and presented in listing format for the Safety Analysis Set. Results from the Modified Medical Research Council (mMRC) dyspnea scale questionnaire will be presented in listing format for the Safety Analysis Set.

### 8.4.3 Prior and Concomitant Medications

Prior and concomitant medications will be coded using World Health Organization (WHO) drug code and summarized separately by Anatomical Therapeutic Chemical (ATC) levels 1, 2 and 4 for the Safety Analysis Set. Prior medications will denote medications used prior to the first dose of study medication. Concomitant medications will denote medications started prior to but continuing after receipt of study medication or medications started after receipt of study medication.

Statistical Analysis Plan	Client/Project	Verona Pharma/RPL554-CO-303
Statistical Analysis Plan	Version and Date	V02 12/11/2024

### 8.4.4 Treatment Compliance

Compliance to study medication will be based on dispensed and returned unused ampules for the safety population. Compliance will be presented for 12 weeks using summary statistics by time intervals (Day 1 to Week 6, Weeks 6-Week 12, and full study length), as well as using frequency counts by subgroups: <80%, 80-90%, 90-100%, >100%.

Compliance with study medication will be calculated on the number of ampules count (total dispensed – total returned) divided by the prescribed number of ampules expressed as a percentage, see calculations below. Patients should take the study medication twice daily. Patients are dispensed ampules at Visit X and return at Visit Y, however in the eCRF returned ampules will be recorded under Visit X.

For time interval compliance to study medication will be calculated as follows:

([N of Ampules dispensed at Visit X] – [N of Ampules returned at Visit Y])/ Denominator1 \* 100 Where Denominator1 is calculated with the following rules:

- N1 = Number of ampules expected. Calculated based on total N of Ampules dispensed at Week 6 and at Week 12, considering 2 ampules per day, apart from first dose (Week 6) or last dose (Week 12) date for completed patients where we would only consider 1 ampule per day calculated: {{[Date of Visit Y] [Date of Dispensing at Visit X] + 1} \* 2 1} for Week 6. Note: this calculation considers the first dose administered on Day 1 at the site is included in the number dispensed for Week 6.
- N2= Number of ampules between dispensing and returning visit calculated: {{[Date of Visit Y] - [Date of Dispensing at Visit X] + 1} \* 2} - 1 for Week 6 and = Number of ampules between dispensing and returning visit calculated: {{[Date of Visit Y] - [Date of Dispensing at Visit X] + 1} \* 2} - 2 for Week 12. Note: this calculation considers the first dose administered on Day 1 at the site is included in the number dispensed for Week 6.
- Week 6 and Week 12 summaries will use N2 for Denominator 1.
- In overall summaries if  $N1 \ge N2$  then Denominator1 = N2.
- In overall summaries if N1 < N2 then Denominator 1 = N1.

Overall compliance to study medication will be calculated 100 times (100\*) the sum of Week 6 and Week 12 compliance divided by the sum of Denominator 1 over Week 6 and Week 12.

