### 6.3.2 Dosing at Home

Subjects will take their study supplied nebulizer and compressor as well as instructions home for use during the study.

Following Visit 2, subjects will self-administer their daily morning and evening doses of study medication at home at approximately the same times each day, approximately 12 hours apart, for 12 weeks.

- Prior to dosing at home, subjects must take their background maintenance COPD medication approximately 2 minutes prior to taking study medication.
- The morning doses of COPD maintenance medication and study medication must be taken at home in the morning prior to Visit 3 and Visit 4.
- Each subject will follow the Nebulizer Set-Up instructions and study medication label to prepare and self-administer the study medication by inhalation using the reusable study supplied nebulizer attached to the study supplied compressor.
- Study medication nebulization time should be approximately 5 to 10 minutes; until a slight sputtering sound from the nebulizer is heard.

Subjects will be instructed as follows:

- Only a study supplied nebulizer and compressor may be used to administer study medication. Only study medication may be used in the study supplied nebulizer and compressor.
- Discard used study medication ampules and open foil pouches of used study medication at home.
- Return unused study medication ampules to the clinic at Visit 3 and Visit 4 for collection, and assessment of medication compliance by a site staff member (Section 6.6).

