## 9.3.5 Other Analyses

Subject disposition including total number of screened subjects, number of completers, withdrawn subjects (including reason for withdrawal) and subjects included in each analysis set will be summarized overall. Subject disposition will be included in subject listings.

The number of subjects with major protocol deviations will be summarized by type and category of violation overall. Major protocol deviations will be included in subject listings.

Demographic and baseline characteristics will be summarized using descriptive statistics overall. Demographic and baseline characteristics will be included in subject listings.

Medical history will be coded using MedDRA and summarized by SOC and PT for each sequence and overall. Medical history will be provided in subject listings.

Prior medications will denote medications used prior to the first dose of study medication. Prior medications will be summarized and provided in subject listings. Prior medications will be provided in subject listings.

Concomitant medications will denote medications started prior to but continuing after receipt of study medication. Concomitant medications will be summarized separately by Anatomical Therapeutic Chemical (ATC) levels 2 and 4. Concomitant medications will be included in subject listings.

Compliance to study medication will be computed based on the number of ampules/foil pouch count dispensed and unused ampules/foil pouches returned. Non-compliance will

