#### Protocol RPL554-CO-303

be defined as a compliance value less than 70% over the full study period. Compliance will be summarized overall.

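### The SAP's overall compliance formula, read literally, divides percentages by ampule counts (118.3% for perfect adherence), and its bands have no cut at the protocol's 70% limit

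*SAP*

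**What the plan says.** SAP 8.4.4 (Treatment Compliance) first gives a general definition: ampules dispensed minus ampules returned, "divided by the prescribed number of ampules expressed as a percentage". For each interval this becomes (dispensed − returned)/Denominator1 × 100.

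Denominator1 is an ampule count, chosen from two quantities:

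- **N2** is (days between visits + 1) × 2, less 1 for the Week 6 interval and less 2 for the Week 12 interval. The interval summaries use N2.
- **N1** is the expected count on twice-daily dosing, with this exception: "apart from first dose (Week 6) or last dose (Week 12) date for completed patients where we would only consider 1 ampule per day". The overall summaries take the smaller of N1 and N2. The second half of that rule reads "In overall summaries if N1 < N2 then Denominator 1 = N1".

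The section's last sentence defines overall compliance as 100 times "the sum of Week 6 and Week 12 compliance divided by the sum of Denominator 1 over Week 6 and Week 12".

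The results go into summary statistics and "frequency counts by subgroups: <80%, 80-90%, 90-100%, >100" per cent.

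Protocol 9.3.5 sets the basis in counts: "Compliance to study medication will be computed based on the number of ampules/foil pouch count dispensed and unused ampules/foil pouches returned". It says that non-compliance will "be defined as a compliance value less than 70% over the full study period". Protocol 6.6 has a second definition, also at 70%, that applies to each visit-to-visit period.

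**The concern.** Within SAP 8.4.4, compliance is the percentage just defined. If the last sentence uses the word in that sense, its numerator is a sum of two percentages and its denominator a sum of ampule counts. The extra factor of 100 then applies to something already multiplied by 100. The result is not a percentage of doses taken. It also depends on how many days fell between visits, so equally adherent subjects can receive different values.

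This sentence is the programming specification for the full-study column of Table 14.1.8. Followed as written, it would give wrong full-study values and wrong band counts there, and in Listing 16.1.9 if that listing uses the same derivation.

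The second issue is independent of the first. The lowest band, <80%, merges subjects below 70% with those from 70% to just under 80%, and the SAP never mentions 70%. Even with a correct formula, the frequency table could not give the number of subjects who are non-compliant by the protocol's own full-study definition. It could not show the per-period definition in Protocol 6.6 either. In addition, the middle bands both include 90%.

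**Working it through.** The documents give no worked compliance figure, so there is nothing to reproduce first.

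**Inputs.** Each interval is 42 ± 3 days (Schedule of Assessments in the SAP and the protocol). N1, N2 and the compliance formulas are from SAP 8.4.4. The background and study doses "must be taken at home in the morning prior to Visit 3 and Visit 4" (Protocol 6.3.2).

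**Denominators on 42-day intervals.**

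- N2, Week 6: (42 + 1) × 2 − 1 = 85.
- N2, Week 12: (42 + 1) × 2 − 2 = 84. This matches a direct count: one evening dose on the day of Visit 3, 41 full days, one morning dose on the day of Visit 4, so 1 + 82 + 1 = 84.
- N1 by the verbal rule: (42 + 1) × 2 − 1 = 85 in each interval. N1 is never below N2, so Denominator1 = N2.
- Sum: 85 + 84 = 169.

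**Perfect adherence, two doses on Day 1 (assumption).** Each interval scores 100%.

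- As written: 100 × (100 + 100)/169 = 118.3%.
- With ampules used in the numerator: 100 × (85 + 84)/169 = 100.0%.
- Entering the interval values as fractions does not help: 100 × 2/169 = 1.18.

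**Perfect adherence, one dose on Day 1.** The subject uses 84 + 84 = 168 ampules, and the intervals score 84/85 = 98.82% and 84/84 = 100%.

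- As written: 100 × 198.82/169 = 117.6%.
- By ampules: 100 × 168/169 = 99.4%.

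**Visit windows, perfect adherence.**

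| Interval lengths (days) | Summed Denominator1 | As written |
|---|---|---|
| 39 + 39 | 79 + 78 = 157 | 127.4% |
| 42 + 42 | 85 + 84 = 169 | 118.3% |
| 45 + 45 | 91 + 90 = 181 | 110.5% |

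**Unequal adherence.** A subject uses 85 of 85 and then 25 of 84 ampules (29.76%).

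- By ampules: 100 × 110/169 = 65.1%, below the protocol's 70%.
- As written: 100 × (100 + 29.76)/169 = 76.8%, above it.

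**Effect on the bands.** With the same adherence *a* (in per cent) in both 42-day intervals, the formula as written gives 200*a*/169. The printed cuts are therefore reached at:

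- 80%: *a* = 80 × 169/200 = 67.6%
- 90%: *a* = 90 × 169/200 = 76.05%
- 100%: *a* = 100 × 169/200 = 84.5%

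A subject at 75% belongs in the <80% band but is shown as 88.8%. A subject at 69% is shown as 81.7%. Everyone above 84.5% falls in the >100% band. Over the permitted windows this last threshold runs from 157/2 = 78.5% to 181/2 = 90.5%.

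**The case against.** The strongest reply is that the intent is plain. The same section opens with dispensed minus returned over the prescribed number, and the closing sentence makes sense only if compliance there means ampules used. A programmer who saw every fully adherent subject above 100% would probably stop and ask, and the table shells, which are in a separate document, may state the derivation correctly. All of that is fair, and it is why the point is minor. It does not make the sentence right: it conflicts with the section's own definition and with Protocol 9.3.5.

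A second reply is that N1 is not fully pinned down. Its printed formula covers Week 6 only and seems to have lost its minus signs when the PDF was read, and the text also ties N1 to ampules dispensed. This stands as a caveat. If N1 were 84 in each interval, the sum would be 168 and the result as written 100 × 200/168 = 119.0%, so the fault remains. The corrected formula would then give 100 × 169/168 = 100.6% for a subject who took all 169 doses.

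On the 70% cut, Protocol 9.3.5 asks only for an overall summary of compliance, the standard statistics in SAP 8.1 include the minimum, and Listing 16.1.9 covers compliance for about 20 subjects. So the information is not lost once the formula is right. A minimum, however, shows whether anyone fell below 70%, not how many.

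**Conclusion.** The concern holds, as a minor one. Taken as written, the overall compliance sentence gives 118.3% for perfect adherence on two 42-day intervals, and 110.5% to 127.4% across the visit windows. It moves subjects across bands and can lift a subject at 65.1% above the protocol's 70% limit. These figures assume two doses on Day 1 where adherence is perfect, and N2 as Denominator1. The band cut points also assume exact 42-day intervals and equal adherence in both.

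The missing 70% cut is a small reporting gap that can be confirmed by reading the two documents together. Neither fault affects an analysis set, an efficacy model or the rule for study success, because none of them uses compliance.

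**What to change.** Replace the last sentence of SAP 8.4.4 with: overall compliance = 100 × [sum over both intervals of (ampules dispensed − ampules returned)] / [sum over both intervals of Denominator1]. Keep the existing rule that takes the smaller of N1 and N2. It would help to print the N1 formula for Week 12 beside the one for Week 6, so that the denominator can be programmed without interpretation.

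Use non-overlapping bands with a cut at 70%, for example <70, 70 to <80, 80 to <90, 90 to 100 and >100. The full-study non-compliance defined in Protocol 9.3.5 can then be read from the table. Applied to the interval columns, the same bands would show the per-period definition in Protocol 6.6.

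The cost is one sentence in SAP 8.4.4, or two if the N1 formula is added, and the bands in SAP 8.4.4 and one table shell. No new data are needed.
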